## Sample size calculation:

The study is powered (80%) to demonstrate non-inferiority following the booster dose of PCV in the 1+1 compared to the 2+1 groups. To control the type I error for the demonstration of non-inferiority for 10 of the 13 PCV13 serotypes or 8 of the 10 PCV10 serotypes, adjustment of the 1-sided alpha was applied ( $\alpha$ =10/13\*0.025 $\approx$ 8/10\*0.025=0.02). Thus the non-inferiority will be declared if the lower limit of the 95% confidence interval for the ratio of the geometric means is greater than 0.5 for at least 10 of the PCV13 serotypes and eight of the PCV10 serotypes. Each 1+1 arm will be compared separately to the 2+1 arm for the specific vaccine formulation.

Sample size calculations assumed: (a) power of at least 80%; (b) two-sided type I error of 0.05; (c) standard deviation of the log antibody concentrations of 0.4; (d) the true ratio of the geometric means to be 1.05; and (e) non-inferiority criteria described above.

A sample size of 91 per group would provide at least 80% power to declare non-inferiority in 10 out of the thirteen PCV13 serotypes or 8 out of the ten PCV10 serotypes (Table 1). The sample size will be adjusted upward by 10% to allow for loss to follow-up and early study withdrawals. The total number to be enrolled will thus be 600, including 300 in the PCV13 cohorts and 300 in the PCV10 cohorts.

Table 1: Sample size calculations based on study definition of non-inferiority, overall power of 80% and a type I error  $\leq 0.05$ .

Computed Sample Size per Group							
Ratio of	Std	Actual Power	Sample Size				
GMC 	Dev 		per Group				
1.25	0.3	0.984	80				
1.25	0.4	0.984	141				
1.25	0.5	0.983	219				
1.25	0.6	0.983	314				
1.12	0.3	0.984	52				
1.12	0.4	0.984	91				
1.12	0.5	0.983	141				
1.12	0.6	0.983	202				
1.00	0.3	0.983	36				
1.00	0.4	0.984	64				
1.00	0.5	0.983	98				
1.00	0.6	0.983	141				

Ratio of GMC = The assumed true ratio of GMC between 1+1 and 2+1 groups. A ratio of 0, 1.12 and 1.25 is equivalent to a 0, 0.05 and 0.10 difference in the log(base 10) antibody concentrations, respectively. Std Dev = standard deviation of the log antibody concentration. It is assumed the standard deviation is the same in both the 1+1 and 2+1 groups.

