## Aims and objectives

## Primary study objective:

 To evaluate the vaccine-serotype specific geometric mean antibody concentrations (GMC) one month following the booster dose (administered at 9 months of age) of differing 1+1 dosing schedule (1st dose at either 6 or 14 weeks of age) compared to the immune response following a 2+1 dosing schedule (6+14 weeks and booster at 9 months) of the same vaccine formulation (i.e. PCV10 or PCV13).

Endpoint: The serotype-specific GMC measured 1 month after the 9-month booster dose for each 1+1 vaccine group and comparing it to the 2+1 group of the same vaccine.

Protocol: PCV1+1, version 2.18 Protocol date: 6th February 2017 Non-inferiority criteria: The lower limit of the 95% confidence interval of the ratio of GMC of the 1+1 and 2+1 dosing schedules being >0.5 for at least 10 of the PCV13 serotypes and eight of the PCV10 serotypes.

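### Scaling alpha by 10/13 or 8/10 does not control the type I error of the 10-of-13 or 8-of-10 claim in its least favourable case, contrary to what the protocol states

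*Protocol*

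**What the plan says.** The primary non-inferiority criterion (Protocol, *Primary study objective*) is a lower 95% confidence limit for the GMC ratio, 1+1 over 2+1, "being >0.5 for at least 10 of the PCV13 serotypes and eight of the PCV10 serotypes". *Sample size calculation* repeats the rule and attaches an error-control statement to it. "To control the type I error for the demonstration of non-inferiority for 10 of the 13 PCV13 serotypes", or for 8 of the 10 PCV10 serotypes, "adjustment of the 1-sided alpha was applied", with 10/13 × 0.025 and 8/10 × 0.025 both written as 0.02.

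The next sentence decides at a different level, and the limit it names is the same margin as in the primary criterion: "Thus the non-inferiority will be declared if the lower limit of the 95% confidence interval for the ratio of the geometric means is greater than" that margin. The planning assumptions include a "two-sided type I error of 0.05" and a "standard deviation of the log antibody concentrations of 0.4". Each 1+1 arm is compared separately with the 2+1 arm of the same formulation. The protocol describes no other multiplicity control.

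**The concern.** The protocol fixes both a formula and what the formula is meant to achieve, so this is a stated property that can be checked, not a detail left to a later plan.

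The claim that a schedule is non-inferior for at least 10 of 13 serotypes is already false when 9 are truly non-inferior and 4 are not. The 9 can pass on merit, and the claim is then made wrongly if any one of the other 4 passes by chance. For PCV10 the same holds with 7 good serotypes and 3 inferior ones. Multiplying alpha by 10/13 or 8/10 bounds a different event: 10 (or 8) chance passes when every serotype is at the margin.

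At stake is the error rate of the primary claim. A false pass would support a reduced schedule although more serotypes are inferior than the rule allows.

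**Working it through.** **Inputs.** From *Primary study objective*: margin 0.5 (log10 2 = 0.301). From *Sample size calculation* and Table 1: rules 10 of 13 and 8 of 10, SD 0.4 on log10, n = 91 per group, planning difference 0.05 log10 (the Table 1 row that gives 91). The text's true ratio of 1.05 does not match that row's 1.12. That is a separate matter and does not affect the error rates. The correlation between serotypes is not given, so values of it below are assumptions.

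**Reproducing the plan.**
- 10/13 × 0.025 = 0.01923; 8/10 × 0.025 = 0.0200.
- Power per serotype: 0.8^(1/13) = 0.983.
- n = 2 × 0.4² × (2.070 + 2.120)² / (0.301 − 0.05)², which rounds up to 90 by the normal formula and 91 by the noncentral t. The t version at 0.01923 reproduces all 12 rows of Table 1. At 0.025, n would be 85–86. The table was therefore built with the scaled alpha.

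**What the scaling does bound.** With all m serotypes at the margin and per-serotype level a, P(at least k passes) ≤ m × a / k under any dependence:
- PCV13: 13 × 0.01923 / 10 = 0.025
- PCV10: 10 × 0.02 / 8 = 0.025

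**Least favourable case.** Put m − k + 1 serotypes exactly at ratio 0.5 and let the rest pass. A false claim needs at least one pass among 4 (PCV13) or 3 (PCV10). If serotypes are independent the error is 1 − (1 − a)^4 or 1 − (1 − a)^3. Under any dependence it is at most 4a or 3a.

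| Level a | PCV13: independent / bound | PCV10: independent / bound |
|---|---|---|
| 0.01923 | 7.5% / 7.7% | – |
| 0.02 | 7.8% / 8.0% | 5.9% / 6.0% |
| 0.025 (95% CI rule as written) | 9.6% / 10% | 7.3% / 7.5% |

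With equal correlation 0.5, 0.8 and 0.9 between serotypes (integrating over a shared normal factor):
- PCV13 at 0.01923: about 6.1%, 4.5%, 3.7%
- PCV10 at 0.02: about 5.1%, 4.0%, 3.4%

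All exceed 2.5%. If the good serotypes pass with only Table 1's probability of 0.984, independently, the figures are 6.5% and 5.3%.

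**How narrow the excess is.** At the adjusted level, over equal correlations from 0 to 0.9:
- Five PCV13 serotypes at the margin, eight passing: 0.4% to 2.4%.
- Four PCV10 serotypes at the margin, six passing: at most 2.1%.
- Four (or three) inferior serotypes at ratio 0.45 instead of 0.5: below 1%. At 0.40: about 0.04% and 0.03%.

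At one-sided 0.025 the same integration gives slightly more: up to 3.1% and 2.7% with one extra serotype at the margin, and up to 1.3% and 0.9% at ratio 0.45.

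**Levels that would give control.** 0.025/4 = 0.00625 and 0.025/3 = 0.00833. The independent-case error is 1 − (1 − 0.00625)^4 = 2.48% and 1 − (1 − 0.00833)^3 = 2.48%, and under any dependence at most 2.5%. With n = 91, SD 0.4 and a 0.05 log10 difference, power per serotype is 0.955 and 0.964. Power of the 10-of-13 rule is 99.8% and of the 8-of-10 rule 99.6% if independent, falling to about 95% under strong correlation. At SD 0.5 the power of the rules is about 73–79%, against 87–97% at the protocol's own level.

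**The case against.** The case against giving this weight is substantial.

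- **The excess is knife-edge.** It needs almost exactly four (or three) serotypes sitting almost exactly at ratio 0.5. This stands. A reader might infer that the scaling protects only when essentially every serotype is inferior. That is too strong: at the adjusted level one more serotype at the margin already brings the error below 2.5% for the correlations examined.
- **No evidence that this case is likely.** A reader might point to the weak first-dose responses in *Introduction and background*: 22% reaching the IgG threshold for 6B, and OPA responses of 14% for 6B and 46% for 23F. These do not support the inference. They name two serotypes, and with two inferior serotypes both claims are true, so no type I error is possible. They also follow a first dose, whereas the endpoint is one month after the booster, and the same section argues that the booster response after one primary dose could be higher.
- **0.02 never governs the decision.** The written rule uses 95% intervals. This is correct, and it is a separate inconsistency. It does not rescue the statement, because the maximum is larger under the written rule.
- **Rules that require k of m serotypes are a legitimate choice.** Agreed. The rule is not in question, only the control attributed to it.
- **Table 1's caption allows a type I error up to 0.05.** The text makes that a two-sided figure, so 0.025 in the direction that matters. Even against 0.05 the independent-case rates are too high, although those at correlation 0.8 or above are not.

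What remains is that type I error control must hold over the whole null, and this case belongs to it.

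**Conclusion.** The statement that the scaled alpha controls the type I error of the primary claim is wrong as written. In the least favourable case the one-sided error per 1+1 arm, against a target of 2.5%, is 7.5% (PCV13, at 0.01923) and 5.9% (PCV10, at 0.02) with independent serotypes. The dependence-free bounds are 7.7% and 6.0%. It is still about 3.7% and 3.4% at an assumed correlation of 0.9. Under the 95% CI rule actually written, the bounds are 10% and 7.5%.

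These figures assume that the inferior serotypes lie at the margin and that the others pass. They are maxima, not expected rates, and the protocol does not show that this configuration is probable. The finding is a false error-control statement on the primary claim. It is not evidence that a false claim is likely, nor an objection to the 10-of-13 and 8-of-10 rules themselves.

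**What to change.** Either of two changes to *Sample size calculation*, with the criterion under *Primary study objective* kept consistent:

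- **(a) Restate.** Delete the statement that the scaling controls the type I error. Give the maximum one-sided error per 1+1 arm of the rule actually used: at most 10% (PCV13) and 7.5% (PCV10) for the 95% CI rule, or 8% and 6% if each serotype is judged at one-sided 0.02. Qualify the type I error in Table 1's caption to match. This costs a few words and nothing in power.
- **(b) Keep the claim of control at 0.025.** Judge each serotype in the success rule at 0.025/4 = 0.00625 for PCV13 and 0.025/3 = 0.0083 for PCV10, that is with two-sided intervals of 98.75% and 98.33%. Report 95% intervals descriptively. Under the planning assumptions no extra children are needed, since power is about 95% to 99.8%. The cost is robustness: at SD 0.5, which Table 1 itself considers, power drops to about 73–79%, below the stated 80%, whereas the protocol's own level gives 87–97%.

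### The primary non-inferiority rule uses an unadjusted 95% CI, although the protocol says a reduced one-sided alpha of about 0.02 was applied and Table 1 was computed at that level

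*Protocol*

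**What the plan says.** Protocol, Sample size calculation. The aim of the adjustment is given as "To control the type I error for the demonstration of non-inferiority for 10 of the 13 PCV13 serotypes or 8 of the 10 PCV10 serotypes", and for that purpose "adjustment of the 1-sided alpha was applied", with the value shown as 10/13 × 0.025 ≈ 8/10 × 0.025 = 0.02. The decision rule follows at once: "Thus the non-inferiority will be declared if the lower limit of the 95% confidence interval for the ratio of the geometric means". The condition placed on that limit is to clear the margin of 0.5 in the required number of serotypes, ten for PCV13 and eight for PCV10. The list of assumptions in the same section then gives "b) two-sided type I error of 0.05".

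Protocol, Primary study objective, non-inferiority criteria. The rule is repeated with the same interval: "The lower limit of the 95% confidence interval of the ratio of GMC of the 1+1 and 2+1 dosing schedules being >0.5", for the same counts of serotypes.

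Neither section gives a 96% interval or any other adjusted interval for the primary criterion.

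**The concern.** A two-sided 95% interval tests each serotype at one-sided 0.025. A one-sided alpha of 0.0192 or 0.02 corresponds to a two-sided interval of 96.15% or 96%. The protocol therefore describes two different primary tests and, by opening the decision rule with the word Thus, presents the unadjusted one as the result of the adjustment.

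Type I error is fixed by the rule used to declare success, not by the alpha used to choose the sample size. Sizing at a smaller alpha buys a little power and gives no error control. An analyst following the primary objective and one following the adjustment sentence would use different thresholds. Because the rule counts serotypes, a single serotype falling between those thresholds could decide the primary conclusion.

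**Working it through.** **Inputs, all from Protocol, Sample size calculation.** Margin: ratio 0.5, which is log10(2) = 0.30103 on the log10 scale. SD of log10 concentration: 0.4. Overall power: 80%. Sample size: 91 per group, equal allocation. Table 1's 91-per-group row is labelled ratio 1.12, which its footnote equates to 0.05 on the log10 scale; the table reproduces when this is taken as a shortfall in the 1+1 arm. The running text instead assumes "the true ratio of the geometric means to be 1.05". That is a separate discrepancy, and the Table 1 row is used here.

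**Step 1: reproduce Table 1.** Two-sample t-test for non-inferiority (noncentral t). Per-serotype power is 0.8^(1/13) = 0.983, which agrees with the 0.983 to 0.984 printed in the table.

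| One-sided alpha | Ratio 1.25, SD 0.3/0.4/0.5/0.6 | Ratio 1.12 | Ratio 1.00 |
|---|---|---|---|
| Table 1 as printed | 80/141/219/314 | 52/91/141/202 | 36/64/98/141 |
| 10/13 × 0.025 = 0.01923 | 80/141/219/314 | 52/91/141/202 | 36/64/98/141 |
| 0.025 (95% CI) | 76/133/207/298 | 49/86/134/192 | 35/60/93/134 |

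All 12 entries match at 0.01923 and none at 0.025. The reduced alpha was therefore used for sizing, and assumption (b) does not describe the calculation behind the table.

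**Step 2: what the adjustment is built to deliver.** If all m serotypes are at the margin and each is tested at alpha, the chance that at least k pass is at most m × alpha / k, whatever the correlation.

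- Adjusted alpha: 13/10 × 0.01923 = 0.025 (PCV13); 10/8 × 0.02 = 0.025 (PCV10).
- 95% CI: 13/10 × 0.025 = 0.0325 (PCV13); 10/8 × 0.025 = 0.03125 (PCV10).

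**Step 3: likely error in the same situation.** The protocol gives no correlation between serotypes, so an equal correlation from 0 to 0.99 is assumed. Simulated chance of a false declaration with 95% CIs and every serotype at the margin:

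| Correlation | 10 of 13 | 8 of 10 |
|---|---|---|
| 0 to 0.3 | below 0.01% | below 0.01% |
| 0.5 | 0.08% | 0.08% |
| 0.8 | 0.7% | 0.7% |
| 0.95 | 1.6% | 1.6% |
| 0.99 | 2.1% | 2.1% |

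Every value is below 2.5%.

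**Step 4: effect on the threshold at n = 91, SD 0.4.** Standard error of the log10 difference = 0.4 × √(2/91) = 0.0593, with 180 degrees of freedom. Smallest passing observed ratio = 10^(−0.30103 + t × 0.0593).

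- 95% CI: t = 1.973, so 10^(−0.1840) = 0.655.
- 96.15% CI: t = 2.085, so 10^(−0.1774) = 0.665.

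**Step 5: power at n = 91 (Table 1 row 1.12, SD 0.4).** Per-serotype power is 0.984 at 0.01923 and 0.988 at 0.025. At 0.025, 86 per group would reach the per-serotype target of 0.983.

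**The case against.** The strongest reply is that little follows in practice. The 3.25% and 3.13% figures are worst-case bounds over every dependence structure, not error rates, and the simulations in step 3 stay under 2.5% with the 95% CI. The two thresholds differ by 0.01 in the observed ratio, and on the plan's assumptions the deciding serotype is unlikely to fall in that band. This stands, and it sets the weight of the point. It does not reconcile the text.

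The heading of Table 1 allows a type I error of up to 0.05, and 3.25% is below that. But a two-sided 0.05 is a one-sided 0.025, so this does not account for the mismatch. It adds one more statement of the target that needs aligning.

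A reader might infer something stronger: that the primary claim carries a false-positive rate near 10%. Suppose exactly 9 PCV13 serotypes are clearly non-inferior, 4 sit exactly at ratio 0.5, and serotypes are independent. The chance that at least one of the four passes is then 1 − 0.975⁴ = 9.6%. This is not the size of the present defect. With the adjusted alpha it is still 1 − (1 − 0.01923)⁴ = 7.5%, so most of it has nothing to do with 95% versus 96.15%. The protocol states a proportional adjustment and does not explicitly promise control in every mixed configuration. The scenario shows only that the proportional adjustment should not be described as giving such control.

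**Conclusion.** The contradiction holds. The protocol claims a one-sided alpha of about 0.02, sized the trial at 0.01923, and declares non-inferiority at one-sided 0.025. The adjustment is absent from the primary test in both places where that test is defined.

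The size is modest: 0.025 against 0.0192 or 0.02 per serotype, and a worst-case bound of 3.25% or 3.13% against 2.5%. The bound needs no assumption about correlation; the finding that simulated error stays below 2.5% rests on equally correlated, normally distributed test statistics with every serotype at the margin. The threshold and power figures rest on "standard deviation of the log antibody concentrations of 0.4" and 91 evaluable children per group.

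The documents do not support reading this as a serious inflation of error or as a fault in the sample size. It should be fixed because it concerns the primary success criterion, which ought to have a single reading before data are seen.

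**What to change.** Choose one of two repairs and apply it in both the Primary study objective and the Sample size calculation.

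1. **Keep the adjustment.** State a 96.15% CI for PCV13 and a 96% CI for PCV10, or 96.15% for both. (A 96% CI for PCV13 would give a bound of 13/10 × 0.02 = 2.6%, slightly over target.) Change assumption (b) to the adjusted one-sided alpha. The size stays at 91 per group, and per-serotype power stays at the 0.984 printed in Table 1.
2. **Keep the 95% CI.** Delete the statement that an adjusted alpha controls type I error, and restate the sample size basis at one-sided 0.025. At that level 86 per group would suffice, and 91 gives per-serotype power of 0.988.

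Under either repair, align the heading of Table 1 with the chosen error level, and do not describe the proportional adjustment as controlling error when some serotypes are truly non-inferior and others are at the margin. If the trial team wants control in that setting, one-sided 0.025/4 for PCV13 (98.75% CI) and 0.025/3 for PCV10 (98.33% CI) would be one way. That is an optional choice of method and not part of this correction.

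The cost is wording in two sections. No additional participants are needed.

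### The true GMC ratio behind 91 per group is misstated: the text gives 1.05 and Table 1 gives 1.12, but 91 requires 1+1 to be about 11% lower than 2+1 (ratio 0.89)

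*Protocol*

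**What the plan says.** The primary objective sets the criterion as the lower 95% confidence limit of the "ratio of GMC of the 1+1 and 2+1 dosing schedules being >0.5". The sample size section repeats it: the lower limit must be "greater than 0.5 for at least 10 of the PCV13 serotypes and eight of the PCV10 serotypes". A lower limit that has to clear 0.5 only makes sense with 1+1 in the numerator.

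Among the planning assumptions, (c) is an SD of 0.4 for the log concentrations and (d) is "the true ratio of the geometric means to be 1.05". The next paragraph takes 91 per group from Table 1. That table has rows for ratios 1.25, 1.12 and 1.00 only. At SD 0.4 they give 141, 91 and 64 per group, so 91 belongs to 1.12, and there is no row for 1.05.

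Footnote 1 of Table 1 defines the ratio as "The assumed true ratio of GMC between 1+1 and 2+1 groups" and adds "A ratio of 0, 1.12 and 1.25 is equivalent to a 0, 0.05 and 0.10 difference in the log(base 10) antibody concentrations".

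**The concern.** There are three problems in one short section.

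- The text and the table give different values, 1.05 and 1.12, for the same assumption.
- The table moves the wrong way for its label. If the ratio is 1+1 over 2+1 and only a low ratio can fail, a true ratio above 1 should need fewer children than a ratio of 1.00. Table 1 needs more: 64, 91 and 141 as the ratio goes 1.00, 1.12, 1.25.
- A ratio of 0, as the footnote has it, is impossible for geometric means. The table row is 1.00.

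The assumed true effect is a core input to a non-inferiority design. Read literally, the protocol presumes that the reduced schedule gives slightly higher antibody than the full one. If the calculation in fact allowed for a deficit, the design is described as resting on the opposite premise, and nobody who checks or reuses it will arrive at 91.

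**Working it through.** **Inputs**

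- Margin: ratio 0.5, i.e. log10(2) = 0.30103 (Primary study objective; Sample size calculation).
- SD: 0.4. I take it as log10, the scale used in footnote 1.
- One-sided alpha: the text says "adjustment of the 1-sided alpha was applied", namely 10/13 × 0.025 = 0.01923, which it rounds to 0.02. Assumption (b), a "two-sided type I error of 0.05", would be 0.025 one-sided.
- Power per serotype: not stated as an input. The Actual Power column reads 0.983 to 0.984, which fits 0.80^(1/13) = 0.98298, that is, 80% overall spread over 13 serotypes treated as independent. This is inferred from the table.

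**Method**

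Two-sample t-test on the log10 scale with n per group. The distance to the margin is δ = 0.30103 + log10(R), with R = (1+1)/(2+1). Power comes from the noncentral t with 2n − 2 degrees of freedom and noncentrality δ / (0.4 × √(2/n)). The required n is the smallest that reaches 0.98298.

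**Step 1: reproduce Table 1**

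With alpha 0.01923 and 1+1 lower by 0, 0.05 or 0.10 log10:

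| 1+1 lower by (log10) | Printed ratio | SD 0.3 | SD 0.4 | SD 0.5 | SD 0.6 |
|---|---|---|---|---|---|
| 0 | 1.00 | 36 | 64 | 98 | 141 |
| 0.05 | 1.12 | 52 | 91 | 141 | 202 |
| 0.10 | 1.25 | 80 | 141 | 219 | 314 |

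All twelve sample sizes match the table, and the achieved powers (0.983 to 0.984) match its Actual Power column. For the chosen row, δ = 0.30103 − 0.05 = 0.25103, n = 91 and power is 0.984. A normal-approximation check gives 2 × 0.16 × (2.070 + 2.120)² / 0.25103² = 89.1, i.e. 90 after rounding up; the t correction brings it to 91.

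So the assumed ratio is 10^-0.05 = 0.891 for the 1.12 rows and 10^-0.10 = 0.794 for the 1.25 rows.

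**Step 2: put in the ratios as written**

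SD 0.4, alpha 0.01923, per-serotype power 0.983:

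| (1+1)/(2+1) | Source | δ | n per group |
|---|---|---|---|
| 1.05 | assumption (d) | 0.3222 | 56 |
| 1/1.05 = 0.952 | assumption (d), inverted | 0.2798 | 73 |
| 1.12 | Table 1 as labelled | 0.3503 | 47 |
| 1.25 | Table 1 as labelled | 0.3979 | 37 |
| 10^-0.05 = 0.891 | 0.05 log10 deficit | 0.2510 | 91 |
| 10^-0.10 = 0.794 | 0.10 log10 deficit | 0.2010 | 141 |

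**Step 3: sensitivity to alpha and power**

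With ratio 1.05, n is 55 at alpha 0.02, 53 at alpha 0.025, and 26 at alpha 0.025 with plain 80% power per serotype. None is near 91. With a ratio of 0.891 and alpha rounded to 0.02, n is 90, so the table used the unrounded alpha.

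**Step 4: what 91 delivers**

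Per-serotype power at n = 91 is 0.984 if the true ratio is 0.891, 0.996 if it is 0.952, and 0.9996 if it is 1.05.

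**The case against.** The strongest reply is that nothing in the trial changes. The 91 per group, the margin and the decision rule all stand. Under a true ratio of 1.05, in either direction, per-serotype power is above the tabulated 0.984. That is correct, and it limits the weight of the point: this is a misdescribed assumption with a conservative consequence, not an undersized trial.

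A second reply is that the direction is merely undefined. Assumption (d) names no numerator, the footnote's log difference carries no sign, and if the column is read as 2+1 over 1+1, Table 1 is coherent. That reading does rescue the table's arithmetic, which is sound in itself. It does not rescue the text as it stands. The same section uses a ratio of geometric means for the rule that the lower limit exceed 0.5, which fixes 1+1 as numerator, and both the primary objective and footnote 1 name 1+1 first. Nor does either direction of 1.05 give 91.

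Two cautions stand. That 1.05 arose from the 0.05 log10 difference is probable, but the protocol does not say so. And nothing in the protocol makes a monitoring decision depend on this ratio, so the harm lies in a misinformed reader and a calculation that cannot be reproduced.

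**Conclusion.** The concern holds. The sample size of 91 rests on a true (1+1)/(2+1) ratio of 0.89, an 11% deficit for the reduced schedule. It does not rest on the 1.05 in the text, which would need 56 (73 if inverted), or on the 1.12 in the table as labelled, which would need 47. This is conditional on SD 0.4 on the log10 scale, one-sided alpha 10/13 × 0.025 and per-serotype power 0.80^(1/13). The last is inferred, but the exact match of all twelve rows leaves little doubt. The error is in the description of the assumption. The sample size is unaffected, and the design is more cautious than its text suggests. It still needs correcting, because it misstates the main planning assumption of the primary comparison.

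**What to change.** - In assumption (d), replace 1.05 with a true ratio (1+1)/(2+1) of 0.89, i.e. 0.05 log10 lower in the 1+1 group.
- In Table 1, relabel the ratio column 1.00, 0.89 and 0.79 in place of 1.00, 1.12 and 1.25. Alternatively, keep the printed values and state that the column is (2+1)/(1+1).
- In footnote 1, change the ratio of 0 to 1.00, name the numerator, and say that the log10 differences are deficits in the 1+1 group.
- While editing, state the unrounded one-sided alpha (0.01923) and the per-serotype power target (0.983), so that a reader can reproduce 91.

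The cost is a correction to one sentence, one table column and one footnote. The 91 per group and the enrolment of 600 do not change.
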